10.5. Appendix 5: Data Display Standards & Handling Conventions

10.5.1. Study Treatment & Sub-group Display Descriptors

Treatment Group Descriptions			
RandAll NG		Data Displays for Reporting	
Code	Description	Description	Order ^[1]
1	FF/UMEC/VI 100mcg/62.5mcg/25mcg + Placebo	FF/UMEC/VI 100/62.5/25	1
2	FF/VI 100mcg/25mcg + UMEC 62.5mcg	FF/VI 100/25 + UMEC 62.5	2

NOTES:

- Order represents treatments being presented in TFL, as appropriate.

10.5.2. Baseline Definition & Derivations

10.5.2.1. Baseline Definitions

Parameter	Study Assessments Collected prior to dosing		Baseline Definition
	Screening	Week 0 (Pre-Dose)	
Efficacy			
Trough FEV1, Trough FVC	X	X	Week 0 pre-dose.
SGRQ total and domain scores		X	Week 0 pre-dose
Safety			
Vitals, Labs, ECGs	X		Most recent individual value prior to first dose (generally Screening but could be a test repeat).

NOTES :

- Unless otherwise specified, the baseline definitions specified in Section [10.5.2.1](#) Baseline Definitions will be used for derivations for endpoints / parameters and indicated on summaries and listings.
- Unless otherwise stated, if baseline data is missing no derivation will be performed and will be set to missing.

10.5.3. Reporting Process & Standards

Reporting Process	
Software	

 The currently supported versions of SAS and TCSG software will be used. 	
Reporting Area	
HARP Server	: UK1SALX00175
HARP Area	: /arenv/arprod/gsk2834425/mid200812/final
QC Spreadsheet	: /arenv/arwork/gsk2834425/mid200812/documents
Analysis Datasets	

 Analysis datasets will be created according to CDISC standards (SDTM Implementation Guide Version 3.1.3 or higher & AdAM Implementation Guide Version 1.0 or higher). For creation of ADaM datasets (ADCM/ADAE), the same version of dictionary datasets will be implemented for conversion from SI to SDTM. 	
Generation of RTF Files	

 RTF files will be generated for the final reporting effort for use in writing the CSR. 	

Reporting Standards	
General	

 The current GSK Integrated Data Standards Library (IDSL) will be applied for reporting, unless otherwise stated: 
 4.03 to 4.23: General Principles 5.01 to 5.08: Principles Related to Data Listings 6.01 to 6.11: Principles Related to Summary Tables 7.01 to 7.13: Principles Related to Graphics 	
Formats	

 All data will be reported according to the treatment to which the subject was randomized unless otherwise stated. However, there may be additional adhoc displays for individual subjects using the actual treatment received. GSK IDSL Statistical Principles (5.03 & 6.06.3) for decimal places will be adopted for reporting of data based on the raw data collected. All data (including data collected post-study treatment discontinuation) will be reported according to the treatment to which the subject was randomized unless otherwise stated. However, there may be additional adhoc displays for individual subjects using the actual treatment received. GSK IDSL Statistical Principles (5.03 & 6.06.3) for decimal places will be adopted for reporting of eCRF data based on the raw data collected. The reported precision from non eCRF sources will follow the IDSL statistical principles but may be adjusted to a clinically interpretable number of decimal places. Percentages between 1% and 99%, inclusive, will be rounded to integers. Percentages greater than 0%, but less than 1%, will be reported as <1%, and percentages greater than 99%, but less than 100%, will be reported as >99%. . Numeric data will be reported at the precision collected on the eCRF. 	

Reporting Standards	

 The reported precision from non eCRF sources will follow the IDSL statistical principles but may be adjusted to a clinically interpretable number of decimal places. 	
Planned and Actual Time	

 Reporting for tables, figures and statistical analyses : 
 Planned time relative to dosing will be used in figures, summaries, statistical analyses and calculation of any derived parameters, unless otherwise stated. Actual time will be used for calculation of times to events and Kaplan-Meier plots. Reporting for listings: 
 Planned and actual time relative to study drug dosing will be shown in listings (refer to IDSL Statistical Principle 5.05.1). Unscheduled or unplanned readings will be presented within the subject's listings. 	
Unscheduled Visits	

 Unscheduled visits will not be included in summary tables except as part of a 'worst case post-baseline' assessment. All unscheduled visits will be included in listings. 	
Descriptive Summary Statistics	
Continuous data	Refer to IDSL Statistical Principle 6.06.1
Categorical data	N, n, frequency, %
Graphical Displays	

 Refer to IDSL Statistical Principals 7.01 to 7.13. 	

10.6. Appendix 6: Derived and Transformed Data

10.6.1. General

Study Day

- Calculated as the number of days from treatment start date :
 - Reference date = missing → Study Day = missing
 - Reference date < treatment start date → Study Day = reference date – treatment start date
 - Reference date ≥ treatment start date → Study Day = reference date – treatment start date + 1

Study Treatment Stop Date

If overall treatment stop date is missing it will be imputed as follows:

- For subjects who attended an Early Withdrawal visit, use the date of the Early Withdrawal visit
- For subjects who attended the last on-treatment visit, use the Visit 5 (Week 24) date
- For subjects who died and did not attend an Early Withdrawal visit or the last on-treatment visit, use the date of death
- For all other subjects, use the last recorded exposure start or stop date

Study and Treatment Completion Definitions

- A subject is considered to have completed the treatment period if they have not prematurely discontinued IP and attended Visit 5.
- A subject is considered to have completed the study if they either attended Visit 5 or had a phone contact at Visit 5.

10.6.2. Study Population

Demographics

Age

- Age will be calculated based on the Pre-screening visit date
- Birth date will be imputed as follows:
 - Any subject with a missing day will have this imputed as day '15'.
 - Any subject with a missing date and month will have this imputed as '30JUN'.
- Birth date will be presented in listings as 'YYYY'.

Age Category

- Age categories are based on age at Pre-screening and are defined as:
 - ≤64 years
 - 65-74 years,
 - 75-84 years
 - ≥85 years

Demographics
Body Mass Index

 Calculated as weight (kg) / [height (m)]²

Subject Disposition
Subject Withdrawal

 For Kaplan-Meier plots of subject withdrawal over time, censoring will be performed as follows: For subject withdrawal, subjects are represented from their Week 0 date to the date of early withdrawal from the study. Subjects that completed the study are censored at the earliest of the date of completion and day 168.
Smoking Status
At Screening, subjects who were identified as former smokers but who last smoked within 6 months prior to Screening will be re-classified as current smokers prior to summarizing. Subject listings will include original and re-classified status.
Compliance

 ELLIPTA™ inhaler A contains FF/UMEC/VI (for subjects in FF/UMEC/VI treatment group) or FF/VI (for subjects in FF/VI+UMEC treatment group) and has container number with prefix 3. ELLIPTA™ inhaler B contains placebo (for subjects in FF/UMEC/VI treatment group) or UMEC (for subjects in FF/VI+UMEC treatment group) and has container number with prefix 4. If a dose counter start count is missing then it will be assumed to be 30. If any dose counter stop is missing then the treatment compliance will be set to missing for that subject and for that inhaler. Number of doses of study drug taken by each subject from each inhaler = Dose counter start-dose counter stop. Compliance are calculated as follows: 
 Compliance for Ellipta inhaler A =(dose counter start – dose counter stop for inhaler A) x 100 / (exposure stop date – exposure start date +1) Compliance for Ellipta Inhaler B=(dose counter start – dose counter stop for Inhaler B) x 100 / (exposure stop date – exposure start date +1) Overall Compliance = (compliance for Inhaler A + compliance for inhaler B with active treatment)/2. That is: 
 For subject in FF/UMEC/VI treatment group, Overall Compliance = compliance for Inhaler A For subject in FF/VI + UMEC treatment group, Overall Compliance = (compliance for Inhaler A + compliance for inhaler B)/2 Overall compliance and compliance for each inhaler will be categorized as follows: 
 < 80 % ≥ 80 % to < 95 % ≥ 95 % to ≤105 % >105 % to ≤120 % >120 %. If a subject received a treatment other than the randomized treatment during the study, the

Subject Disposition
compliance will still be calculated using data from all containers received and overall exposure start and stop dates.
Long-acting Bronchodilator Usage During the Run-in (Randomisation Stratum)

Randomization stratum, long-acting bronchodilator usage during the run-in, will be derived based on the RMC classification and will be grouped into the following 3 categories:
 
 • None • One long-acting bronchodilator per day • Two long-acting bronchodilators per day 
Long-acting bronchodilator is defined as any COPD medication in Respiratory Medication Class (MRC) under 'Long-acting beta-2 agonist – Group 2' or 'Long-acting beta-2 agonist – Group 3' or 'Long-acting anticholinergic'.
 
Based on RAMOS NG record, the number of subjects used none long-acting bronchodilator during run-in is very small (ie. <1% of randomized subjects). Therefore, the combined stratum with 2 categories will be used in the statistical analysis, ie, none and one long-acting bronchodilator per day will be combined into one category in analysis.
 
Ranodmisation stratum is also collected at randomization in RAMOS NG. Both randomization stratum (derived and collected) will be listed.

Medical Conditions and Concomitant Medications
Cardiovascular Risk Factors

Subjects with at least one of the following current or past medical conditions at Screening will be classed as having a cardiovascular (CV) risk factor at screening. The number of CV risk factors at Screening (0, 1, or ≥2) will be derived.
 
 • Angina pectoris • Coronary artery disease • Myocardial infarction • Arrhythmia • Congestive heart failure • Hypertension • Cerebrovascular accident • Carotid or aorto-femoral vascular disease, • Diabetes mellitus • Hypercholesterolemia
COPD Concomitant medications

COPD concomitant medications will be grouped into the following RMCs based on pre-defined code lists derived from ATC classifications:
 
 • Antiinfectives (antibiotics, antifungals, antivirals, antiseptics) • Short-acting anticholinergic

Medical Conditions and Concomitant Medications

• Short-acting beta-2 agonist• Long-acting anticholinergic• Long-acting beta-2 agonist• Xanthine• PDE4 Inhibitor• Corticosteroid - inhaled• Corticosteroid - depot• Corticosteroid - systemic oral parenteral and intra-articular• Corticosteroid - other• Leukotriene receptor antagonist• Nedocromil or cromolyn sodium• Mucolytic• Oxygen• Other medication given for exacerbation• Other COPD medication
COPD medication combination

COPD medications taken on the day of the Screening visit will be grouped into the following categories based on the RMC classification:
 
• ICS• LABA• LAMA• Xanthine• PDE4 Inhibitors• Any combination of the above• Other• None

Medical Conditions and Concomitant Medications**COPD Exacerbation History**

- Individual exacerbations during the 12 months prior to Screening and during the study were to be collected on the eCRF by the Investigator.
- COPD exacerbations with onset date on or after the date of Screening will not be included in the counts of number of exacerbations in the past year; all other exacerbations recorded on the eCRF will be included in the counts, even if onset/resolution dates are missing or earlier than the start of the exact 12 month period prior to Screening.
- COPD exacerbations reported in the past 12 months will be categorized as 0, 1, 2, ≥ 3
- Number of COPD exacerbations reported in the past 12 months prior to Screening will be summarized according to three categories: moderate COPD exacerbations, severe COPD exacerbations and moderate/severe COPD exacerbations.
 - Moderate COPD exacerbations are defined as exacerbations that required treatment with systemic/oral corticosteroids and/or antibiotics (not involving hospitalization).
 - Severe COPD exacerbations are defined as exacerbations that required in-patient hospitalization.
- Total number of moderate/severe COPD exacerbations are defined as total numbers of moderate and severe COPD exacerbations for each subject.
- Summaries of moderate/severe exacerbations by treatment course are defined as exacerbations treated with systemic/oral corticosteroids (with or without antibiotics), and exacerbations treated with antibiotics (with or without systemic/oral corticosteroids).

Medical Conditions and Concomitant Medications
COPD Assessment Test (CAT) at Screening
CAT Score
The CAT consists of eight items each formatted as a six-point differential scale: 0 (no impact) to 5 (high impact). A CAT score will be calculated by summing the non-missing scores on the eight items with a range from 0 to 40. If one item is missing, then the score for that item is set as the average of the non-missing items. If more than one item is missing, then the CAT score will be set to missing. The CAT score at screening will be summarized.
CAT Category
Subject will be classified into the following CAT category based on the CAT score at Screening: 
 • CAT <10 • CAT ≥10 The CAT category at screening will be summarised

Baseline Lung Function
Reversibility
The reversibility to salbutamol status of a subject is calculated at Screening and is based on the difference (absolute change and % change) between a subject's pre-salbutamol assessment of FEV1 and their post-salbutamol assessment FEV1 and is defined as follows: 
 • Reversible, if they had a difference in FEV1 of ≥ 12% and ≥ 200 mL, or • Non-reversible, if they had a difference in FEV1 of < 200 mL or a ≥ 200 mL difference that was < 12 % of the pre-salbutamol FEV1.
GOLD Grade 1-4 at Screening
Subjects will be classified into Global Initiative on Obstructive Lung Disease (GOLD) Grades 1-4 using the post-salbutamol percent predicted FEV1 assessment at Screening: 
 • GOLD Grade 1 (Mild): percent predicted FEV1 ≥ 80% • GOLD Grade 2 (Moderate): 50% ≤ percent predicted FEV1 < 80% • GOLD Grade 3 (Severe): 30% ≤ percent predicted FEV1 < 50% • GOLD Grade 4 (Very Severe): percent predicted FEV1 < 30%

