Subjects in subset A will provide a blood sample at two time-points at Week 12 (V4) and at Week 24 (V5). Subjects in subset B will provide blood samples at seven time points at Week 12 (V4).

Subjects providing PK samples for subset A may also be asked to take part in a hair sample, scalp & finger secretion PK Sub-Study. See [Appendix 8](#) (Section 12.8).

A subject will be considered to have completed the study when they have completed all phases of the study including screening, run-in, the randomised treatment phase, and safety follow-up. Subjects who stop study treatment early will complete an Early Withdrawal Visit, followed by a Safety Follow-Up a week later and finally be withdrawn from the study.

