10.7. Appendix 7: Premature Withdrawals & Handling of Missing Data

10.7.1. Premature Withdrawals

Element	Reporting Detail
General	
 For reporting purposes, subject study completion (i.e. as specified in the protocol) was defined as a subject will be considered to have completed the study when they have completed all phases of the study including screening, run-in, randomization, the randomized treatment phase up to visit 5 and safety follow-up visit. Withdrawn subjects will not be replaced in the study. All available data from subjects who were withdrawn from the study will be listed and all available planned data will be included in summary tables and figures, unless otherwise specified.
Vitals/Lab/ECG	
 Vitals/Lab/ECG data collected as part of the early withdrawal at a scheduled visit, or at a standalone EW visit will be used in the summary of absolute values and change from baseline as part of the ‘minimum post baseline’, ‘minimum change from baseline’, ‘maximum post-baseline’ and ‘maximum change from baseline’ for diastolic and ‘maximum post-baseline’ and ‘maximum change from baseline’ for pulse rate and systolic blood pressure

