10.13.4. Study Population Figures

Study Population figures			
No.	Populatio n	Title	Deliverable
1.1.	ITT	Kaplan-Meier Plot of Time to Study Withdrawal	SAC

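### The time-to-withdrawal plot stops counting completers at day 168 but sets no limit for withdrawals, so one withdrawal dated after day 168 takes the curve to 100% withdrawn

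*SAP*

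**What the plan says.** The display is SAP Figure 1.1, "Kaplan-Meier Plot of Time to Study Withdrawal", for the ITT population. SAP 10.6.2 gives its derivation in two sentences. The first covers the events: "For subject withdrawal, subjects are represented from their Week 0 date to the date of early withdrawal from the study". The second covers the censored subjects: "Subjects that completed the study are censored at the earliest of the date of completion and day 168". SAP 10.5.3 adds: "Actual time will be used for calculation of times to events and Kaplan-Meier plots". Day 168 is therefore compared with real dates, not nominal visit weeks.

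On late dates, protocol 4.1 says that subjects who stop treatment early have an Early Withdrawal Visit, "followed by a Safety Follow-Up a week later and finally be withdrawn from the study".

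Study completion is defined in two ways. SAP 10.6.1: "A subject is considered to have completed the study if they either attended Visit 5 or had a phone contact at Visit 5". SAP 10.7.1, which presents itself as the protocol's definition for reporting purposes, requires all phases, including "the randomized treatment phase up to visit 5 and safety follow-up visit". Protocol 5.6 also requires the follow-up call or visit.

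**The concern.** Events and censoring do not share a time limit. Completers leave the risk set by day 168 at the latest, while a subject who withdraws on day 170 or 180 stays in it until that date. A Kaplan-Meier step equals events divided by subjects at risk. Once the completers have gone, each remaining subject is a future event, so the last step is always one event out of one at risk.

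Readers use a withdrawal plot to judge retention and missing data, which matters in a non-inferiority trial. A curve that runs flat at a modest withdrawal rate and then drops to zero retained misstates what happened.

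The SAP avoids this elsewhere. For time to first exacerbation, on-treatment events are counted up to the treatment stop date plus one day (10.4.2), and event-free subjects are censored at that same limit or at death (10.6.4). The withdrawal plot has no matching rule.

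The two completion definitions add an ambiguity. A subject who attends Visit 5 but misses the safety follow-up is a completer under SAP 10.6.1 but not under SAP 10.7.1 or protocol 5.6. Under the latter two, that subject could be a withdrawal dated after day 168.

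**Working it through.** The plan states no numerical result for this figure, so there is nothing to reproduce. The check is whether dates after day 168 can arise, and what the stated rule then produces.

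**Can withdrawals fall after day 168?**
- SAP 10.6.1 sets study day = date − treatment start + 1. Week 24 is 24 × 7 = 168 elapsed days, which is study day 169.
- The Visit 5 window is −8/+6 days (time and events tables): 169 − 8 = 161 to 169 + 6 = 175. If day 168 is read as elapsed days, the window is 160 to 174, which still passes the cap.
- Follow-up is one week later, −1/+4 days. The latest date is 175 + 7 + 4 = 186 and the earliest is 161 + 7 − 1 = 167.
- If withdrawal is dated at the follow-up step in protocol 4.1, an Early Withdrawal Visit on day 162 gives 162 + 7 = 169.
- The SAP does not say which recorded date is the withdrawal date. Protocol 4.1 gives a sequence of steps, not a date derivation.

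Dates after day 168 are therefore possible. How often they occur is not stated.

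**What does the rule produce?** S(t) is the product of (1 − d/n) over event times, where d is events and n is subjects at risk.

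*Illustration with 530 per arm.* The region counts in SAP 10.8.1 are 398 + 252 + 215 + 194 = 1059, or about 530 per arm at 1:1. Assume 42 withdrawals before any completer is censored, 487 completers censored by day 168, and one withdrawal on day 172 (42 + 487 + 1 = 530). The 42 and the day are assumptions.
- Day 168: 1 − S = 42/530 = 7.9%.
- Day 172: n = 1, d = 1, so S is multiplied by (1 − 1/1) = 0 and 1 − S = 100%.

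*Range with 510 per arm (1020/2 from protocol 9.2.1).* Early withdrawals all fall by day 160, before any completer is censored.

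| Withdrawn by day 160 | Before any late withdrawal | After one on day 170 |
|---|---|---|
| 25/510 | 4.9% | 100% |
| 51/510 | 10.0% | 100% |
| 102/510 | 20.0% | 100% |

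With several late withdrawals and 102/510 early:
- Two: 1 − 0.8 × 1/2 = 60%, then 100%.
- Three: 1 − 0.8 × 2/3 = 46.7%, then 1 − 0.8 × 2/3 × 1/2 = 73.3%, then 100%.
- None: no distortion. A withdrawal on day 168 itself does no harm, because completers censored that day still count as at risk.

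**What does a consistent rule give?** Take 102/510 early withdrawals plus one on day 170. Capping everyone at day 168 ends the curve at 102/510 = 20.0%. Keeping completers at risk to a common end (day 186) ends it at 103/510 = 20.2%, the crude proportion. Both are sensible summaries; 100% is not.

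**The case against.** The strongest reply is that little depends on this figure. It is descriptive, with no test or estimate attached. Missing data can be judged from visit attendance (Table 1.2), treatment discontinuation (1.3), study withdrawal (1.4), exclusions from the modified per-protocol population (1.12) and the tipping-point analysis. A statistician would recognise a vertical drop with one subject at risk as a tail artefact, and the curve is sound up to day 168. Graphics conventions are delegated to sponsor standards that are not reproduced in the SAP and might truncate the axis. All of this stands as a limit on importance. It does not rescue the written rule, because nothing in the protocol or SAP censors later withdrawals or ends the axis at day 168.

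Three stronger readings are tempting, and the documents do not support them.

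- *The collapse is almost certain.* Spreading withdrawal dates uniformly over days 1-186 gives, with 5% withdrawing, 1 − (1 − 0.05 × 18/186)^530 ≈ 92%. But under SAP 10.6.1 attending Visit 5 already makes a subject a completer, and day 186 is reached only as the follow-up to an attended Visit 5. Assume instead a constant hazard, Visit 5 spread evenly over days 161-175, and withdrawal only before Visit 5. With 5% to 12% withdrawing by day 168, the chance of a late withdrawal in an arm of 530 is about 20% to 39% if dated at stopping, and about 61% to 88% if dated a week later. The spread shows that the answer is set by assumptions the documents do not fix.
- *The figure misstates retention by arm.* The title of Figure 1.1 does not say that curves are drawn by arm, whereas SAP 8.1.2.4 does say so for exacerbations. A single overall curve collapses in the same way.
- *The withdrawal counts in Table 1.4 are wrong.* The censoring rule does not touch them. SAP 10.7.1 points to the protocol's completion definition for reporting, and SAP 6.1.1 describes an end-of-study record summary, so a shift in those counts is not established.

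**Conclusion.** The point holds as a minor one. Under the rule as written, any single withdrawal dated after day 168 takes the curve in Figure 1.1, overall or by arm, to 100% withdrawn whatever the true rate: 7.9% becomes 100% in the 530-subject illustration. That consequence is exact and needs only one such date. The visit window and follow-up schedule make the date possible; the documents do not say how likely it is.

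The damage is limited to one descriptive figure. The conflict between the completion definitions is real but secondary. It matters here because it decides whether a subject who attends Visit 5 and misses follow-up is censored or may be plotted as a late event.

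**What to change.** In SAP 10.6.2, apply one limit to both sides: censor at day 168 every subject still in the study on that day, including those who withdraw later, and plot as events only withdrawals dated on or before day 168. State which recorded date is the withdrawal date, and whether day 168 is a study day or elapsed days.

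Censoring completers at their actual completion date instead is only a partial remedy. The risk set would still thin across the Visit 5 and follow-up windows, and a withdrawal near the end would still produce an inflated step.

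Align SAP 10.6.1 with protocol 5.6 and SAP 10.7.1 so that one definition decides who is a completer in Figure 1.1. If completion is then dated at follow-up, the earliest in-window date is day 167, so nearly all completers stay at risk up to the cut-off.

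The cost is a few sentences and a small change to the derivation. The one downside is that withdrawals after day 168 leave the figure and appear only in Table 1.4 and the listings; a footnote giving their number would cover that.
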